4.5.9.2 Total Functional Capacity Scale

The TFC is a validated measure of global patient function in HD. The TFC represents the investigator's assessment of the patient's capacity to perform a range of activities of basic daily living, including working, chores, managing finances, eating, dressing, and bathing. The 5-item assessment is based on a brief interview with the patient and the study companion (if available). The TFC score ranges from 0 to 13, with a higher score representing better functioning. A 1-point change in TFC score is a clinically meaningful change in patient function (e.g., a 1-point decline may indicate the loss of ability to work in a normal capacity) (Huntington Study Group 1996). The TFC takes approximately 10 minutes to administer and will be completed at clinic visits.

4.5.9.3 Total Motor Score

The TMS is a holistic measure of motor function in HD that is linked to both functional capacity based on the TFC score, independence, and driving status (Beglinter et al. 2012; Schobel et al. 2017).

The TMS score is the sum of the individual motor ratings obtained from administration of the 31-item motor assessment portion of the UHDRS by the investigator. The score ranges from 0 to 124, with a higher score representing more severe impairment. The TMS takes approximately 15 minutes to administer and will be completed at clinic visits.

4.5.9.4 Symbol Digit Modalities Test

The SDMT is used to assess attention, visuoperceptual processing, working memory, and psychomotor speed. It has been shown to have strong reliability and validity (Smith 1982). The patient pairs abstract symbols with specific numbers according to a translation key. The test measures the number of items correctly paired (maximum of 110 correct pairs) in 90 seconds. The SDMT will be administered at clinic visits and can be completed in less than 5 minutes. It will also be administered at specified timepoints *indicated in Appendix 6* on the Roche HD mobile app (via electronic SDMT).

4.5.9.5 Stroop Word Reading Test

The SWR Test is a measure of attention, processing, and psychomotor speed and depends upon quick verbal motor output. Patients are presented with a page of color names (i.e., "BLUE," "RED," or "GREEN") printed in black ink and are asked to read aloud as many words as possible within a given amount of time (in 45 seconds). The number of words read correctly is counted, with a higher score indicating better cognitive

performance. It will also be administered at specified timepoints *indicated in Appendix 6* on the Roche HD mobile app (via electronic SWR).

4.5.9.6 UHDRS Functional Assessment

The UHDRS Functional Assessment is a checklist of 25 common daily tasks. The investigator indicates if the patient can perform the task by giving a score of 1 to all "yes" replies. The checklist is then summed, and scores can range from 0 (inability to do any task) to 25 (ability to do all tasks on the checklist). The UHDRS FA can be completed in 15 minutes.

4.5.9.7 Independence Scale

A patient's IS score is a measure of disease progression in functional disability and will be completed to evaluate a patient's degree of independence at screening and at specified timepoints. It is a subscale of the UHDRS. The scale consists of 19 discrete levels ranging from 10 to 100 (by 5), in which a score of 100 indicates no special care is needed and a score of 10 indicates the patient is fed by tube and requires total bed care.

4.5.9.8 HD Daily Activities Scale

The HD-DAS assesses patients' daily function. Following a semi-structured interview with the patient and/or study companion, the patient's ability level to perform daily tasks such as eating or using a telephone will be recorded. Each item is scored on a 4-point Likert-type scale, where 0 indicates no impact and 3 indicates severe impact.

4.5.9.9 Clinical Global Impression, Severity and Change Scales

The CGI-S is a single-item measure of current global severity and is completed by the clinician at specified clinic visits. The CGI-S is assessed using an 11-point numeric rating scale (NRS), where higher scores indicate greater severity. The CGI-S can be completed in approximately 2 minutes.

The CGI-C is a single-item measure of change in global status (since starting the study) and is completed by the clinician at specified postbaseline visits. The CGI-C has seven response options: "very much worse," "much worse," "minimally worse," "no change," "minimally improved," "much improved," and "very much improved." The CGI-C can be completed in approximately 2 minutes. To assess the relevance of this change, a follow-up question with dichotomous response options ("yes" or "no") asks if the change has had a meaningful impact on the patient's well-being.

4.5.9.10 Patient Global Impression, Severity and Change Scales

The PGI-S is a single-item measure of current global severity and is completed by the patient at specified clinic visits. The PGI-S can be completed in approximately 2 minutes. The PGI-S is assessed using an 11-point NRS, where higher scores indicate greater severity.

The PGI-C is a single-item measure of change in global status (since starting the study) and is completed by the patient at specified post-baseline visits. The PGI-C has seven response options: "very much worse," "much worse," "minimally worse," "no change," "minimally improved," "much improved," and "very much improved." To assess the relevance of this change, a follow-up question with dichotomous response options ("yes" or "no") asks if the change has had a meaningful impact on the patient's well-being. The PGI-C can be completed in approximately 2 minutes.

4.5.9.11 Companion-Reported Global Impression, Severity and Change Scales

The Companion-Reported Global Impression–Severity (CrGI-S) is a single-item measure of current global severity and is completed by the companion (about the patient) at specified clinic visits. The CrGI-S can be completed in approximately 2 minutes. The CrGI-S is assessed using an 11-point NRS, where higher scores indicate greater severity.

The Companion-Reported Global Impression–Change (CrGI-C) is a single-item measure of change in global status (since starting the study) and is completed by the companion (about the patient) at specified post-baseline visits. The CrGI-C has seven response options: "very much worse," "much worse," "minimally worse," "no change," "minimally improved," "much improved," and "very much improved." To assess the relevance of this change, a follow-up question with dichotomous response options ("yes" or "no") asks if the change has had a meaningful impact on the patient's well-being. The CrGI-C can be completed in approximately 2 minutes.

4.5.9.12 Montreal Cognitive Assessment

The MoCA is a patient-completed assessment used to detect cognitive impairment. It contains a series of basic assessments, including attention and visuospatial tasks. The total score ranges from 0–30, where lower scores indicate greater impairment. It will be used in this study to characterize patients at screening and longitudinally to assess cognitive status at regular intervals throughout the study. It takes approximately 10 minutes to administer.

4.5.9.13 Work Productivity and Activity Impairment

The WPAI contains 6 items assessing the impact of disease on employment status (yes/no), hours missed due to disease, hours missed due to other reasons, hours worked, and impact on productivity and on daily activities (both using an 11-point NRS, where higher scores indicate greater impact). The WPAI takes approximately 5 minutes to complete. The WPAI will be completed by the patient (about him/herself) and by the study companion (if available, about him/herself). It will be completed at specified timepoints remotely by the patient on the Roche HD mobile app and by the study companion (if available) on an electronic device.

4.5.9.14 Apathy Evaluation Scale

The AES is an 18-item assessment of apathy, including overt behavior, cognitive aspects of motivation, and emotional responsivity. Each item is scored on a 4-point Likert scale, from 1 ("Not at all") to 4 ("A lot"). A total score is created by summing the 18 items (scores range from 18 to 72; 3 items are reverse scored), with higher scores indicating greater apathy. The AES takes approximately 10 minutes to complete and will be completed by the patient and study companion (if available) at specified clinic visits.

4.5.9.15 Neuro-QoL Cognition Function Short Form, Version 2

The Neuro-QoL Cognition Function Short Form contains 8 items (including "trouble concentrating" and difficulty "learning new tasks or instructions"), each assessed using a 5-point Likert scale, where lower scores indicate greater difficulty (4 items) or greater frequency (4 items). The raw sum score is converted to a T-score distribution (mean=50, standard deviation=10). The Neuro-QoL Cognition Function Short Form takes approximately 5 minutes to complete and will be completed by the patient at specified clinic visits.

4.5.9.16 HD Speaking Difficulty Item

The HD-SDI includes a single question assessing difficulty speaking over the past 7 days. It is assessed using a 5-point Likert scale, where higher scores indicate a greater frequency of difficulty. The HD-SDI can be completed in less than 1 minute and will be completed at specified timepoints remotely by the patient on the Roche HD mobile app.

4.5.9.17 Symptoms of Major Depressive Disorder Scale

The SMDDS is a newly developed, valid, and reliable self-report assessment of depression (McCarrier et al. 2016). It contains 16 items, measuring concepts such as sadness, irritability, worry, and sleep disturbance. Each item is assessed on a 5-point Likert scale, from "Not at all" to "Extremely" (9 items) and from "Never" to "Always" (7 items). Item scores from 15 of the items (the least severe of the two eating items is not included) are summed to create a 0–60 score, where higher scores indicate more severe depressive symptomatology. The SMDDS takes approximately 10 minutes to complete and will be completed by the patient at specified clinic visits.

The patient should be referred for immediate psychiatric evaluation in any event of suspected active suicidal intent, significant suicidal behavior, or clinical finding suggesting that the patient is dangerous to himself or herself.

4.5.9.18 HD Companion-Reported Irritability and Angry Outbursts Scale

The HD-CIAOS is a study companion-reported assessment of the patient's irritability and angry outbursts over the past 7 days and will be completed at specified timepoints remotely by the companion (if available) on an electronic device. It consists of three items: frequency of irritable behavior (6-point Likert scale: "Not at all" to "Always"), frequency of angry outbursts (number of occurrences), and severity of the worst outburst

(4-point Likert scale "Mild" to "Very severe"). The HD-CIAOS takes about 2 minutes to complete.

4.5.9.19 EuroQol 5-Dimension, 5-Level Questionnaire

The EQ-5D-5L is a validated self-report health status questionnaire used to calculate a health status utility score for use in health economic analyses (EuroQol Group 1990; Brooks 1996; Herdman et al. 2011; Janssen et al. 2013). There are two components to the EQ-5D-5L: a 5-item health state profile that assesses mobility, self-care, usual activities, pain/discomfort, and anxiety/depression, as well as a VAS that measures health state. Published weighting systems allow for creation of a single composite score of the patient's health status (Index score) from the 5-item scores (i.e., does not include the VAS). The EQ-5D-5L takes approximately 5 minutes to complete. The Index score will be used in this study for informing pharmacoeconomic evaluations. The VAS score will be used to assess health-related quality of life (HRQoL). The EQ-5D-5L will be completed both by the patient (about him/herself) and by the study companion (if available, about him/herself) at baseline and at specified post-baseline clinic visits on an electronic device. In addition, it will be completed remotely at specified timepoints by the patient on the Roche HD mobile app and by the study companion on an electronic device.

4.5.9.20 Health Utilities Index Mark 2 and Mark 3

The HUI® is a multi-attribute system of health status (Feeny et al. 1995). The HUI2 and HUI3 questionnaire (commonly referred to as HUI2/3) contains 15 items with Likert-type response options. From these items, two scores can be produced: HUI2 (7 items) and HUI3 (8 items). Both scores are health utility indexes, where 0=death, and 1=perfect health.

The HUI2/3 will be completed by the companion, both about him/herself and as a proxy report of the patient's HRQoL. The HUI2/3 will be completed at specified timepoints at clinic visits and remotely on an electronic device.

4.5.9.21 Columbia-Suicide Severity Rating Scale

The C-SSRS is a structured tool to assess suicidal ideation and behavior. Four constructs are measured: severity of ideation, intensity of ideation, behavior, and lethality of actual suicide attempts. Binary (yes/no) data are collected for 10 categories, and composite endpoints based on the categories are followed over time to monitor patient safety (Posner et al. 2011). It maps to the Columbia-Classification Algorithm for Suicide Assessment and meets the criteria listed in the U.S. FDA draft guidance for assessment of suicidality in clinical trials (FDA 2012). The C-SSRS will be used to assess eligibility for the study (full version at baseline, requiring approximately 20 minutes to administer) and to monitor the patients throughout the study at clinic visits (follow-up version, requiring approximately 5 minutes to administer, assuming absence of suicidal ideation and no change in clinical status from previous administration).

The patient should be referred for immediate psychiatric evaluation in any event of suspected active suicidal intent, significant suicidal behavior, or clinical finding suggesting that the patient is dangerous to himself or herself.

4.5.9.22 Optional Exit Interviews

Optional exit interviews will be conducted with a subset of patients (up to 60 patients) at select sites within approximately 1 week after the end-of-treatment visit. The semi-structured interviews will be conducted by an external vendor and can be conducted by telephone. The interviews will enable patients to provide details about changes they observe in their symptoms, as well as any impacts on daily life.

Interviews will be transcribed verbatim, and themes emerging from these transcripts will be interpreted in relation to changes in patients' clinical outcome assessment scores. All participants in this optional study interview will be asked which arm they thought they were assigned to (120 mg Q8W, 120 mg Q16W, or placebo). Of note, patients, staff, and the Sponsor will remain blind to patient treatment assignment during the study, as outlined in Section [4.2](#).

Additional consent for this optional portion of the study will be included in the relevant Informed Consent Form.

4.5.9.23 Roche HD Mobile Application: Remote Testing (Smartphone and Wrist-Worn Wearable)

Smartphones and wrist-worn wearables have high-quality sensors that enable the remote, non-invasive, frequent, and precise measurement of motor and non-motor symptoms (Maetzler et al. 2013; Andrzejewski et al. 2016; Adams et al. 2017; Lipsmeier et al. 2018). Each patient will receive a preconfigured smartphone and wrist-worn wearable with installed software for the Roche HD mobile app assessments. The devices and software will monitor motor symptoms, non-motor symptoms, and activities associated with routine daily living throughout the course of the study. Additional details are available in the Roche HD mobile app (Smartphone) manual.

Patients will be provided with devices and trained on their use during screening. *Patients will also have in-clinic assessments of the digital platform that are supervised as indicated in [Appendix 6](#). Outside of the clinic, patients will be instructed to conduct an "active test" every day at approximately the same time (ideally in the morning, after breakfast). The active test consists of a short, preconfigured schedule of tasks that assess motor symptoms (upper and lower body movements, upper limb dexterity, voice) and non-motor symptoms (processing speed, voice). Testing will usually last approximately 5 minutes in total on a typical day of testing. Not all tests are daily. Additional information on the tasks and schedule is specified in [Appendix 6](#).*

For "passive monitoring," patients will be instructed to carry the smartphone in a manner convenient to them (e.g., in a pocket or in a Sponsor-provided pouch) and wear the

wrist-worn wearable throughout the day as they go about their daily routines. Companions (where available) will receive their own independent electronic device at screening, which is different from the patient smartphone.

Patients will be encouraged to adhere to the daily schedule of tasks as much as possible; however, patients will not be excluded from the study for poor adherence, nor will missing a daily test be considered a protocol deviation.

Device sensor data will be recorded continuously, throughout the active tests and passive monitoring. Sound will only be recorded during selected active test tasks. Data will be encrypted and uploaded to secure servers when the smartphone is connected to Wi-Fi. Patients will be asked to charge the devices overnight. If patients have a Wi-Fi network at home, they will be encouraged to connect their smartphone to enable data transfer. If no Wi-Fi network is available, the sensor data will be transferred during clinic visits or after the devices have been returned.

Roche HD mobile app "baseline" data will consist of all data collected prior to and including the baseline visit (up to 28 days). Baseline data will be collected for at least the 7 days up to and including Day 1.

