3. STUDY DESIGN

3.1 DESCRIPTION OF THE STUDY

3.1.1 Overview of Study Design

Study BN40423 is a Phase III, randomized, placebo-controlled, double-blind, multicenter clinical study to evaluate the efficacy, safety, PK, and biomarker effects of intrathecally administered RO7234292 in patients with manifest HD.

Prospective patients will undergo screening assessments during a 4-week screening period. A maximum of one re-screening will be allowed within 8 weeks of the initial screening failure for patients who fail the initial screening (see Section 4.5.1).

Upon completion of the screening period, eligible patients will be randomly allocated in a 1:1:1 ratio to receive RO7234292 Q8W (RO7234292 Q8W arm), RO7234292 Q16W (RO7234292 Q16W arm), or placebo Q8W (placebo arm) by IT injection, as described

in [Table 1](#). To maintain the study blind and integrity, patients in the RO7234292 Q16W arm will also receive placebo (i.e., alternating doses of active drug and placebo).

Table 1 Treatment Regimens after Implementation of Protocol Version 4

Arm	Treatment Regimen
RO7234292 Q8W arm	RO7234292 loading dose: 120 mg at Days 1 and 29 (2 doses) RO7234292: 120 mg Q8W from Week 13 to Week 93 (11 doses)
RO7234292 Q16W arm	RO7234292 loading dose: 120 mg at Days 1 and 29 (2 doses) RO7234292: 120 mg Q16W from Week 21 to Week 85 (5 doses) Placebo: Q16W from Week 13 to Week 93 (6 doses)
Placebo arm	Placebo: at Days 1 and 29 (2 doses) and Q8W from Week 13 to Week 93 (11 doses)

Q8W=every 8 weeks; Q16W=every 16 weeks.

During scheduled clinic visits, patients will undergo safety and tolerability evaluations that include neurologic examinations, vital signs, ECGs, clinical laboratory tests, MoCA, C-SSRS, neuroimaging assessments (neurologic safety sequences), and a review of any adverse events including related concomitant medications, as detailed in [Appendix 1](#).

If there is the occurrence of a failed IT bolus dosing procedure due to inadequate establishment of access to the IT space, a second dosing attempt may occur up to 7 days after the originally scheduled dosing visit. At this additional visit, safety and tolerability evaluations will be performed as described in [Appendix 1](#).

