Patients will be discouraged from resting supine after the lumbar puncture procedure and will be encouraged to mobilize immediately by walking around at a minimum and, if feasible, walking briskly for approximately 30 minutes. Patients should not perform any activity that is associated with a change in the ambient air pressure for at least 72 hours postdose (e.g., air travel, scuba diving, or hot air balloons).

Lumbar punctures will be performed as specified in the schedule of activities (see [Appendix 1](#)), with the last CSF sample obtained at the Week 101 end-of-treatment visit. No study drug will be administered at that visit.

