4.5.9.24 Roche HD Mobile Application: In-Clinic Assessments

Patients will be instructed to bring the smartphone and wearable to every clinic visit to check adherence and technical status of the devices. At specified clinic visits, patients will be asked to conduct the "active test" tasks under the supervision of trained site staff, as shown in [Appendix 6](#).

The smartphone and wearable must be returned to the clinic in cases where the patient does not meet eligibility criteria, at the end of the study, or upon early termination from the study. At the time of study completion or early termination, patients will be asked to complete a pen-and-paper satisfaction survey about their experience using the smartphone and wrist-worn wearable.

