ADA=anti-drug antibody; AES=Apathy Evaluation Scale; BL=baseline; CGI-C = Clinical Global Impression, Change; CGI-S = Clinical Global Impression, Severity; CrGI-C=Companion-Reported Global Impression, Change; CrGI-S=Companion-Reported Global Impression, Severity; CRQ=Companion-reported questionnaire; CSF=cerebrospinal fluid; C-SSRS = Columbia-Suicide Severity Rating Scale; cUHDRS = composite Unified Huntington's Disease Rating Scale; DCL=diagnostic confidence level; eCRF = electronic Case Report Form; EoT = end of treatment; EQ-5D-5L=EuroQol 5-Dimension, 5-Level Questionnaire; ETT=early treatment termination; FA=Functional Assessment; HBsAg=hepatitis B surface antigen; HCV=hepatitis C virus; HD=Huntington disease; HD-CIAOS=Huntington's Disease Companion-Reported Irritability and Angry Outbursts Scale; HD-DAS=HD Daily Activities Scale; HUI=Health Utilities Index; MoCA = Montreal Cognitive Assessment; MRI = magnetic resonance imaging; Neuro-QoL = Quality of Life in Neurological Disorders; PGI-C = Patient Global Impression, Change; PGI-S = Patient Global Impression, Severity; PK=pharmacokinetic; Q8W=every 8 weeks; RBR = Research Biosample Repository; SDMT=Symbol Digit Modalities Test; SFU = safety follow-up; SMDDS = Symptoms of Major Depressive Disorder Scale; SWR = Stroop Word Reading; TFC = Total Functional Capacity Scale; TMS = Total Motor Score; UHDRS=Unified Huntington's Disease Rating Scale.

Notes: All assessments should be performed at the scheduled visit, unless otherwise specified. On treatment days, all assessments should be performed prior to dosing, unless otherwise specified.

- ^a A maximum of one re-screening will be allowed within 8 weeks of the initial screening failure for patients who fail the initial screening (e.g., as a consequence of abnormal laboratory values or general medical status not meeting inclusion or exclusion criteria). If re-screening is required, CAG repeat length testing does not need to be repeated and the screening MRI and viral serology from the initial screening, *including for other Roche studies*, may be acceptable as part of the re-screening assessments, if performed within 12 weeks of the baseline visit.

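### The Roche HD mobile app baseline has no predose cut-off, so passive sensor data recorded after the first injection on Day 1 count as baseline for an exploratory endpoint

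*Protocol*

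**What the plan says.** Section 4.5.9.23 of the protocol fixes the baseline window for the app in two sentences. Baseline "data will consist of all data collected prior to and including the baseline visit (up to 28 days"). Then: "Baseline data will be collected for at least the 7 days up to and including Day 1". Neither sentence gives a time of day or mentions the dose.

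The same section describes the recording: "Device sensor data will be recorded continuously, throughout the active tests and passive monitoring". Patients are told to wear the "wrist-worn wearable throughout the day as they go about their daily routines". Section 4.5.9.24 brings the devices to the clinic: "Patients will be instructed to bring the smartphone and wearable to every clinic visit to check adherence and technical status of the devices".

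Table 1 in Section 3.1.1 puts the first injection on Day 1. For both active arms it reads "RO7234292 loading dose: 120 mg at Days 1 and 29 (2 doses"), and the placebo arm is injected on the same days. After the puncture, Section 4.5.5 says that patients are "encouraged to mobilize immediately by walking around at a minimum and, if feasible, walking briskly for approximately 30 minutes". Appendix 8 also presumes a 30-minute walk before the postdose neurological examination.

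The predose rules are these:
- The notes to Appendix 1: "On treatment days, all assessments should be performed prior to dosing, unless otherwise specified".
- Section 4.5.9 places in-clinic outcome data before the lumbar puncture.
- Appendix 4, Table 2, footnote a, requires the supervised app session (Block 5) to be finished before the dose at baseline.

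Appendix 1 lists the remote app stream only as continuous collection.

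The endpoint that uses this baseline is the Week 101 change in the app's sensor-based measures, one of the exploratory efficacy endpoints in Section 2.1.3.

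**The concern.** A change-from-baseline measure needs a reference taken before treatment. The predose rules quoted above show that the protocol intends this for scheduled outcome assessments, including the supervised app test. For the continuous stream, Section 4.5.9.23 sets a different window that runs past the first injection.

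The hours after an intrathecal injection are not ordinary hours. The patient is in clinic and is encouraged to walk, and may have pain or headache. Section 5.1.1 reports procedural pain in 54% and post-lumbar puncture syndrome in 37% of patients in the Phase I/IIa study. Section 5.1.1.1 reports headache after 10% of procedures. Sensors meant to capture motor symptoms and daily activity would record those hours as the patient's usual state. The result is a noisier baseline for passive measures and, if the drug had any acute effect, a baseline that already contains part of it.

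**Working it through.** The protocol states no figure to reproduce. The check has two parts: whether any rule removes the post-injection data, and what share of the baseline they make up.

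**Does any rule remove them?**

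| Data on Day 1 | Rule that applies | Predose? |
|---|---|---|
| Supervised in-clinic app test | Appendix 4, Table 2, footnote a; Section 4.5.9 | Yes |
| Unsupervised daily active test | Section 4.5.9.23: ideally in the morning, not tied to the dose | Usually, not assured |
| Passive phone and wearable stream | Section 4.5.9.23; continuous in Appendix 1 | No cut-off |

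The general note in Appendix 1 governs when an assessment is performed. A stream that is always running is not performed at a point in time, so the note does not cut it. If the baseline visit is read narrowly as the time spent in clinic, the evening of Day 1 is less clearly included. The injection and the walk still lie inside the visit, and the second sentence names Day 1 itself.

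**What share?**

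Inputs from the protocol: a window of 7 to 28 days (Section 4.5.9.23); puncture ideally between 08:00 and 15:00 (Section 4.5.5); a walk of about 0.5 h (Section 4.5.5).

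Input assumed: 16 h of wear per day, 07:00 to 23:00. The protocol gives no wear time.

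Post-injection hours on Day 1 = 23:00 minus puncture time:
- puncture at 08:00: 15 h
- puncture at 15:00: 8 h

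Total wear = 16 h × days: 16 × 7 = 112 h; 16 × 28 = 448 h.

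Share = post-injection hours / total wear:

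| | 7-day baseline | 28-day baseline |
|---|---|---|
| Puncture at 08:00 | 15/112 = 13.4% | 15/448 = 3.3% |
| Puncture at 15:00 | 8/112 = 7.1% | 8/448 = 1.8% |
| Walk alone | 0.5/112 = 0.45% | 0.5/448 = 0.11% |

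With equal wear on every day, the share cannot exceed Day 1's share of the window: 1/7 = 14.3% or 1/28 = 3.6%. Ending the window at the first puncture makes the post-injection share 0%.

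**The case against.** The best case against the point is that this is data handling for one exploratory endpoint. Section 6.6.5 plans only summaries with optional modelling for such endpoints. The protocol defines no passive feature, and Section 6 leaves analysis detail to the SAP. A filter may well be written there. This bears on importance, but the protocol has not left the matter open: it states a window, and that window includes post-injection data.

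Several stronger readings are tempting, and the documents do not support them.

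- *The whole sensor baseline is contaminated.* It is not. The supervised tapping, drawing, chorea, balance, U-turn and cognitive tasks are predose at baseline.
- *The app is the only assessment not held to a predose rule.* Neurologic examinations are also done after dosing (Section 4.5.3), and Week 37 PK samples are taken at 1, 2 and 4 hours postdose (Appendix 1, footnote p).
- *All of Day 1 is lost to the procedure, and the baseline mean moves by several percent.* The hours before the puncture are valid, and the protocol gives no figure for how far Day 1 activity departs from usual, so no shift in the mean can be stated.
- *The walk is the main problem.* It is encouraged where feasible and makes up under 0.5% of wear time.
- *The treatment comparison is biased.* Placebo patients have the same puncture, injection and walk, so a common procedural shift cancels between arms. An acute drug effect is not shown in patients: Section 5.1.2.1 reports no adverse trends in neurological examinations in Phase I/IIa. The transient reflex changes in monkeys also occurred in controls, with slightly higher incidence at high dose.

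**Conclusion.** The point stands in a limited form. Read as written, Section 4.5.9.23 counts as baseline the passive sensor data recorded after the first injection on Day 1, and any unsupervised active test done later that day. Under the 16-hour wear assumption this is about 7% to 13% of a 7-day baseline and 2% to 3% of a 28-day baseline. The expected consequence is added noise in passive measures of one exploratory endpoint. Between-arm bias would arise only with an acute drug effect. No primary or secondary efficacy result depends on it. It is a minor correction, worth making because it is nearly free.

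**What to change.** Amend Section 4.5.9.23 so that app baseline consists of data time-stamped before the first lumbar puncture and injection on Day 1, reaching back at most 28 days. Keep the present minimum window ending on Day 1 and drop only the post-injection part of that day. Requiring seven full predose days would lengthen the run-in and is not needed.

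The cost is one sentence, a time-stamp filter that uses the clock time of the first puncture, and the loss of roughly 8 to 15 hours of Day 1 recording per patient under the same wear assumption. No visit, assessment or sample size changes.
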